Initial communication with the each study site will include an all-staff meeting to inform staff of the study, entry criteria and plan. The purpose of this meeting is to ensure adequate knowledge of staff about the study for referral of study subjects.

Continued communication with the PPMM and FPA site investigators and coordinators will occur routinely through e-mail and monthly through planned conference calls. Issues with recruitment, specimen collection and study progress will be discussed.

15) Sharing of Results with Subjects

Study results will not be shared with subjects or their primary physicians. Outcomes for PPMM Sacramento B Street Clinic patients who expel the pregnancy during the two-week treatment period will be shared with the PPMM Sacramento B Street Clinic study team. Outcomes for FPA Sacramento Clinic patients who expel the pregnancy during the two-week treatment period will be shared with the FPA Sacramento Clinic study team.

16) Provisions to Protect the Privacy Interests of Subjects

All conversations during enrollment and clinical care will be in private clinic spaces as per usual practice. During screening, research staff will review that the study is voluntary and that demographic questions can be skipped. Remaining aspects of the enrollment visit are clinically necessary and will be treated similarly to a standard clinical visit. It will be reinforced that study participation or declination will not change the patient's medical care.

Baseline history questions and pre-operative interview ensure medically safe abortion procedures and give providers information about offering additional social support to women who may benefit. We interview all women to confirm they are making an autonomous decision to terminate a pregnancy and are not being coerced. As Family Planning specialists, our physicians are trained to provide appropriate and thoughtful care to women seeking abortions and there are no deviations in interview practices from standard clinical care for the research described here.

Electronic medical records will only be accessed, addended, or reviewed when clinically necessary. Participants will be notified of this and research staff will review and sign an institutional HIPAA release to grant this access.

PROTOCOL TITLE: A Randomized Trial of Mifepristone Antagonization with High-Dose Progesterone to Prevent Medical Abortion

17) Compensation for Research-Related Injury

The University of California, Davis Health System will provide care needed to treat injuries directly resulting from taking part in this research. Insurance or third party payers may be billed, if appropriate, for the costs of the care subjects received. Subjects may be responsible for some of the costs. The University of California, Davis does not plan to compensate subjects for injuries.

18) Economic Burden to Subjects

The subject is responsible for costs related to abortion care. The subject will not be responsible for any costs related to study participation. Study participation requires additional visits to the UCD Ambulatory Care Center and may incur transportation cost or additional time away from work.

19) Drugs or Devices

I confirm that all investigational drugs will be received by the Investigational Drug Service (IDS). The IDS will store, handle, and administer those drugs so that they will be used only on subjects and be used only by authorized investigators.

20) [ClinicalTrials.gov](#) Registration

Section 1: NIH Funded Studies

If yes to BOTH, the study must be registered on Clinicaltrials.gov.

Yes
 This study is funded by the NIH . (If this study is not funded by NIH, go to Section 2.)
 One or more human subjects will be prospectively assigned to one or more interventions (which may include placebo or other control) to evaluate the effects of those interventions on health-related biomedical or behavioral outcomes.

Section 2: Studies subject to FDA jurisdiction

If yes to ANY the study must be registered on Clinicaltrials.gov.

Yes
 This is a prospective clinical study of health outcomes in human subjects that compares an intervention with an FDA-regulated device against a control. This is not a small clinical trial to determine the feasibility of a device, or a clinical trial to test prototype devices where the primary outcome measure relates to feasibility and not to health outcomes.
 This is a pediatric postmarket surveillance of a device as required under section 522 of the Federal Food, Drug, and Cosmetic Act.

PROTOCOL TITLE: A Randomized Trial of Mifepristone Antagonization with High-Dose Progesterone to Prevent Medical Abortion

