 - b. Significant anemia – known recent hemoglobin <9.5 gm/dL

PROTOCOL TITLE: A Randomized Trial of Mifepristone Antagonization with High-Dose Progesterone to Prevent Medical Abortion

- c. Clinically significant cardiovascular disease (angina, valvular disease, arrhythmia, or congestive heart failure)
- d. Breastfeeding
- e. Coagulopathy or therapeutic coagulation
- f. Ultrasound evidence of molar or ectopic pregnancy
- g. Chronic systemic corticosteroid use
- h. Adrenal disease
- i. Sickle cell anemia with frequent/recent crises
- j. Glaucoma

- 2. IUD in place during conception, even if removed.
- 3. Peanut allergy.
- 4. Known intolerance of mifepristone or progesterone.
- 5. Any other condition, that in the opinion of the clinician, would contraindicate mifepristone, progesterone or medical abortion.

Pregnant women will be included in this research. This study evaluates effect of high-dose progesterone on initiation of medical abortion and only pregnant women can have an abortion. Potential subjects must have gone through appropriate informed consent for surgical abortion per the standard of care within the UCD Department of Obstetrics and Gynecology prior to consent and screening for this research trial.

5) Study Timelines

Subject participation: approximately 15-17 days

Study timeline

- Duration of enrollment: 11 months (Anticipate Feb 2019 through Dec 2019)
- Completion of primary analysis: 2 months after completion of follow-up (Anticipate Feb 2020)

6) Study Endpoints

Primary endpoint: continuing pregnancy with presence of gestational cardiac activity after two weeks of study treatment

Secondary endpoints:

- Expulsion rates over two weeks following mifepristone treatment
- Pathology changes in trophoblast in a subset of dilation and curettage specimens
- Change in hCG and progesterone levels during treatment
- Tolerability of treatment
 - Ability to continue treatment for two weeks
 - Adverse events (side effects) related to progesterone or placebo after mifepristone including but not limited to nausea, vomiting, headache, mood changes, cramping, vaginal spotting, vaginal bleeding

PROTOCOL TITLE: A Randomized Trial of Mifepristone Antagonization with High-Dose Progesterone to Prevent Medical Abortion

- Safety outcomes: adverse events related to medical safety (e.g., hemorrhage, emergency department visits, emergent dilation and curettage procedures)

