- On days 3 and 4, take the study treatments about 12 hours apart, one dose in the morning and one in the evening.
- On day 5 through the end of the study, take the study treatment in the morning, at about the same time every day.
- Subjects will be provided with:
 - A daily diary to mark down use of the study drug, adverse effects, and bleeding. The diary will also include information on baseline pregnancy symptoms (present when she started the study). Subjects will be instructed to mark down any adverse effects (e.g., nausea, headache, mood changes) on the back of the diary; for any pregnancy symptom present at baseline, the subject will be instructed only to mark down if this symptom becomes worse than baseline.
 - An information sheet with study office phone numbers and instructions related to expected bleeding and cramping should the pregnancy expel after mifepristone treatment.
- Study day 2: the study site will contact the subject by phone around the time that study treatment is supposed to be started.
- Follow-up Visits: schedule on study days 4 (± 1 day) and 8 (± 1 day) at UCD Family Planning Research office.
 - Diary will be reviewed.
 - Study drug container will be reviewed and remaining drug counted by study staff.
 - The subject will be asked if she is tolerating the treatment and willing to continue study participation.
 - Two 5 mL tubes of blood will be obtained for serum hCG and progesterone level.
 - Ultrasonography will be performed to evaluate for presence of the gestational sac, interval growth and presence of gestational cardiac activity; the exam should preferentially be performed vaginally unless the gestational age or subject anatomy requires abdominal sonography for clearer visualization.
 - If gestational cardiac activity is absent, the visit will be considered an exit visit.
 - Collect remaining study drug and diary.
 - Refer subject to the original referral source (PPMM, FPA or the UCD Family Planning clinic) for completion of follow-up care; a patient from PPMM or FPA can request to complete care at UCD.
 - Referrals for PPMM-referred subjects returning to PPMM will be made to the Sacramento B Street Clinic.
 - Referrals for FPA-referred subjects returning to FPA will be made to the Sacramento Clinic.

PROTOCOL TITLE: A Randomized Trial of Mifepristone Antagonization with High-Dose Progesterone to Prevent Medical Abortion

- The subject will be exited from the study after a final outcome is determined by the clinical team.

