8) Data and/or Specimen Management and Confidentiality

Sample size:

- Delgado and colleagues estimate the oral progesterone regimen in this study has an efficacy of 68% (10) and that about 25% of women will expel the pregnancy after mifepristone 200 mg treatment alone, (10,12) implying an effect size of ~43%.
 - Sample size needed for Effect1=68%, Effect2=25%, Alpha=0.05, Beta=0.20: 20 per group.
 - Sample size needed for Effect1=70%, Effect2=25%, Alpha=0.05, Beta=0.20: 18 per group.
- We plan a convenience sample of 40 women (approximately 20 per group) which is enough to answer the primary question of efficacy proposed by Delgado and colleagues.
 - Should no obvious benefit be observed then a larger trial would not be indicated.
 - If some benefit is present, then a sample size could be estimated for a larger trial with considerations of sample size estimates for different gestational age ranges.
 - Importantly, if we cannot feasibly recruit from this population, then a larger study would also need to consider alternative mechanisms for enrollment.
- Recruitment: expect 36 subjects from PPMM and FPA (competitive enrollment) and 4 subjects from UCD.

Data Analysis Plan:

We will include all women randomized and perform intent-to-treat analysis with no apparent exclusions. In addition, a second analysis will be conducted with a per-protocol population, excluding women who do not report ingesting the study medication per protocol. Evaluations will include primary outcome (continuing pregnancy), expulsion rates, adverse effects, and treatment continuation rates.

At time of enrollment, we will collect baseline demographic data, including age, race, ethnicity, education level, and medical history (including obstetric and gynecologic history).

PROTOCOL TITLE: A Randomized Trial of Mifepristone Antagonization with High-Dose Progesterone to Prevent Medical Abortion

Fisher's Exact Testing will be used to compare outcomes and baseline characteristics in the two groups.

While not powered to detect a statistically significant difference among the two groups for secondary outcomes, exploratory analyses will be performed to identify possible trends and areas of interest for a subsequent larger trial. Chi square and Fisher's Exact Tests will be utilized to compare dichotomous variables as appropriate.

Data Management Plan:

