The mifepristone label does not provide side effects for mifepristone alone; side effects are provided for the combination of mifepristone and misoprostol. The data,

PROTOCOL TITLE: A Randomized Trial of Mifepristone Antagonization with High-Dose Progesterone to Prevent Medical Abortion

especially as it relates to bleeding, does not reflect just mifepristone use. Data on mifepristone side effects are taken from reference #19.

Nausea	39%
Cramping	27%
Headache	20%
Dizziness	20%
Warmth/chills	19%
Vomiting	14%
Spotting	9%
Diarrhea	7%

For this study, we expect bleeding and/or spotting to occur in all subjects (even though most will not expel the pregnancy).

2. Progesterone side effects:

From the Prometrium label – use in premenopausal women at 400 mg/day

Dizziness	24%
Abdominal Pain (Cramping)	20%
Headache	16%
Breast Pain	16%
Infection Viral	12%
Musculoskeletal Pain	12%
Fatigue	8%
Abdominal Distention (Bloating)	8%
Diarrhea	8%
Nausea	8%
Back Pain	8%
Irritability	8%
Coughing	8%

3. Teratogenicity: if women decide to continue the pregnancy after receiving one or both study treatments, mifepristone and progesterone are not considered teratogens.

Teratogenicity with standard medical abortion treatment is related to misoprostol, which is not being used in this study.

4. Pregnancy expulsion: few women expel the pregnancy with mifepristone 200 mg treatment in medical abortion studies. However, few studies follow women for up to 2 weeks. We do not know the spontaneous expulsion rate with this treatment but expect the rate may be around 30%; Delgado and colleagues estimate the oral progesterone regimen in this study has an efficacy of 68% (10) meaning that at least ~30% will expel the pregnancy, even with progesterone treatment.

If pregnancy expulsion occurs, the woman will experience bleeding and cramping. The cramping can be very strong for several hours and is typically treated with NSAIDs. Subjects will be made aware that if they need stronger pain medication they can contact the physician on call. Initial bleeding may be similar to, or greater than, a

PROTOCOL TITLE: A Randomized Trial of Mifepristone Antagonization with High-Dose Progesterone to Prevent Medical Abortion

heavy period and may include blood clots and tissue. Within a few hours bleeding is usually equal to or less than a typical menses. After passing the pregnancy, bleeding or spotting can be expected for an average of 9-16 days and may last for up to 30 days.

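### Cramping and bleeding count as study-drug side effects with no rule to separate them from symptoms of pregnancy loss, so an efficacy difference could appear as a tolerability difference

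*Combined protocol and SAP*

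**What the plan says.** - **Endpoint.** Section 6 (Tolerability of treatment) takes as side effects those "related to progesterone or placebo after mifepristone including but not limited to nausea, vomiting, headache, mood changes, cramping, vaginal spotting, vaginal bleeding". Expulsion is a separate secondary endpoint in the same list.
- **Cause of the same symptoms.** Section 12, item 4: "If pregnancy expulsion occurs, the woman will experience bleeding and cramping". Section 12, item 1: "we expect bleeding and/or spotting to occur in all subjects (even though most will not expel the pregnancy").
- **Data source.** Section 7 gives each woman "A daily diary to mark down use of the study drug, adverse effects, and bleeding". On follow-up visits it says: "If gestational cardiac activity is absent, the visit will be considered an exit visit". The same holds when the pregnancy has been expelled, and the diary is collected at that visit.
- **Analysis.** Section 8 analyses all randomized women, with a second per-protocol analysis: "Evaluations will include primary outcome (continuing pregnancy), expulsion rates, adverse effects, and treatment continuation rates". Outcomes are compared with Fisher's exact test. Secondary comparisons are called exploratory and unpowered, and are meant to guide a larger trial.
- **Attribution.** Section 10 has an investigator review each adverse event for relation to study drug. Under section 7 the study team is blinded to allocation. No section says how cramping or bleeding around a loss is to be classified.

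**The concern.** Two of the listed side effects, cramping and bleeding, are also how an expulsion presents. The trial's hypothesis is that losses differ by arm. If it is true, the arm with more losses collects more of these symptoms whether or not the capsules cause any. This is unlike the symptoms that mifepristone causes in both arms, which dilute a comparison without tilting it.

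Two misreadings are at stake. Progesterone could seem to reduce cramping when it has only reduced losses. Or a real increase in cramping caused by progesterone could be cancelled or reversed. Either would mislead the planning of the larger trial that these exploratory analyses are meant to inform.

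**Working it through.** **The plan's own figure.** The documents give no figure for the side-effect comparison. The design rates used below come from the sample size in section 8, which reproduces. For 68% v 25%, two-sided 0.05, 80% power and pooled variance:

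n = [1.96·√(2·0.465·0.535) + 0.8416·√(0.68·0.32 + 0.25·0.75)]² / 0.43² = (1.3825 + 0.5357)² / 0.1849 = 19.9, so 20 per group, as stated.

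Section 3 says 25% would continue without treatment, while section 8 says 25% would expel. The 43-point effect fits only the section 3 reading, which is used here. The two sections must be reconciled.

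**Inputs.**
- Loss: 1 − 0.25 = 75% on placebo, 1 − 0.68 = 32% on progesterone.
- Background cramping b = 27% in women who do not expel (mifepristone side-effect table, section 12).
- Assumed: a share f of losses are expulsions with cramping marked in the diary, f from 0.5 to 1. The documents do not give f.
- No effect of progesterone on cramping.

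**Formula.** P(cramping) = L·f + (1 − L·f)·b, with L the loss rate. The difference, placebo minus progesterone, is (0.75 − 0.32)·f·(1 − b). The last column is the exact probability that Fisher's test rejects at 20 per arm.

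| f | Placebo | Progesterone | Difference | Fisher rejects |
|---|---|---|---|---|
| 0.5 | 0.375 + 0.625·0.27 = 54.4% | 0.16 + 0.84·0.27 = 38.7% | 15.7 points | 9% |
| 1.0 | 0.75 + 0.25·0.27 = 81.8% | 0.32 + 0.68·0.27 = 50.4% | 31.4 points | 46% |

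With 27% in both arms and no loss symptoms, the expected difference is 0 and Fisher's test rejects in 2.4%.

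**Masking.** Let progesterone raise cramping by 20 points in non-expelling women (27% to 47%).
- f = 0.5: 0.16 + 0.84·0.47 = 55.5% v 54.4%, shown as +1 point.
- f = 1: 0.32 + 0.68·0.47 = 64.0% v 81.8%, shown as −18 points.

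**Sensitivity to the background rate.** The cited source for the 27% is a comparison of misoprostol 6 to 8 hours v 24 hours after mifepristone, so its window may be about a day, not two weeks. With b = 40% the artefact is 0.43·f·0.60 = 13 to 26 points. With b = 60% it is 0.43·f·0.40 = 9 to 17 points.

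**Sensitivity to the expulsion rate.** Section 12 expects about 30% expulsion with mifepristone and about 30% even with progesterone.
- At 30% v 32% expulsion, the difference is 0.02 × (cramping with expulsion − b). With 60-100% cramping at expulsion and b of 20-40%, this is 0.4 to 1.6 points, with placebo lower.
- If 30% is the placebo expulsion rate within a 75% loss rate, then f = 0.30/0.75 = 0.4. The same share on progesterone gives 12.8% expelling. Cramping is 48.9% v 36.3%, a difference of 12.6 points.

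**Bleeding.** Section 12 states that "we expect bleeding and/or spotting to occur in all subjects". At 100% in both arms, a yes/no comparison has an expected difference of 0. Only the amount or duration of bleeding can carry the artefact.

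**Follow-up.** Visits are on days 4 (±1), 8 (±1) and 15-17. Expulsion cramping precedes the visit that finds the loss, so the diary already holds it when collected. Women with a loss then exit early. Any-occurrence counts of other symptoms, such as nausea, therefore come from fewer days in the arm with more losses.

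**The case against.** The strongest reply has four parts.

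1. **Relatedness review.** The endpoint is restricted to events related to study drug, and a blinded investigator who knows the scan result could attribute expulsion cramping to the expulsion. This stands in part: it may remove some events, so a reader should not infer that an efficacy difference will be reported as a side-effect difference. But no criterion is written. Section 12 gives three sources of cramping: mifepristone (27%), progesterone (20% on its label) and expulsion.
2. **Window.** A reader might infer that symptoms are compared over all diary days. The documents do not say so. The window is unspecified, and the diary ends at the visit that finds the loss.
3. **Diary instruction.** For symptoms present at baseline, "the subject will be instructed only to mark down if this symptom becomes worse than baseline". A reader might take this as a one-way bias. It is ordinary adverse-event recording: section 10 includes worsening of a pre-existing condition in its definition, and relief of a symptom is not an adverse event. This is not part of the point.
4. **A valid description.** Comparing all symptoms as randomized tells what women experience. Expulsion is reported separately, and the comparison is exploratory with about 20 per arm. This stands, and is why the all-randomized table should stay. Reporting expulsion separately does not, however, take its symptoms out of the side-effect counts.

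**Conclusion.** The point holds in a limited form. The plan counts symptoms of pregnancy loss as study-drug side effects and has no window, split or attribution rule to separate them. At the design rates of 68% v 25%, a cramping comparison could show about 16 to 31 points in favour of progesterone with no drug effect, or turn a true 20-point increase into +1 to −18 points.

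The size rests on 27% background cramping, on 50-100% of losses being expulsions with cramping, and above all on a real difference in expulsion between arms. At about 30% expulsion in both arms the artefact is about 0 to 2 points. The point concerns cramping and the amount or duration of bleeding. A reader might extend it to any bleeding or spotting, but the protocol expects that in every woman. Because the endpoint is secondary and exploratory, the primary analysis is unaffected. What is affected is whether the tolerability result can be interpreted.

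**What to change.** In the Data Analysis Plan (section 8):

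1. Keep the side-effect table in all randomized women, and keep cramping within tolerability. Removing it would hide a drug effect.
2. Add a table of cramping and bleeding by arm and pregnancy outcome, split into before loss and at or after loss. Date the loss from the diary where possible. Otherwise use the interval between the last scan with cardiac activity and the visit that found the loss. Cutting at the last such scan alone would not do: a woman whose loss is found at the day-4 visit was last scanned on day 1, before her first capsule on day 2, and would contribute no time.
3. Also give side effects per diary day from the first capsule, separately for days 2-4 and later days, because early exits shorten follow-up.
4. State that a cramping difference is interpreted only together with the expulsion result.

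**Cost.** A few sentences, using the diaries and scans already planned. Section 7 has adverse effects marked on the back of the diary and does not say that each is dated, so per-day counts depend on dated entries. The cells will be small, the dating of loss imprecise, and the split is on a post-randomization event that the drug may influence. The added table is therefore descriptive and not a basis for testing.

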Study enrollment, outcomes and safety events will be reviewed continuously by the investigative team and in formal Family Planning Research meetings approximately twice monthly to monitor for events that would indicate safety issues.

7) Procedures Involved

Design: Double-blind placebo-controlled study of the effects of oral micronized progesterone on the viability of early pregnancies treated with mifepristone.

Study Treatment: Subjects will receive mifepristone 200 mg on Study day 1. Intervention treatment of micronized progesterone 200 mg capsules or placebo in a labeled container will be started on Study day 2.

- The UCD Investigational Drug Service (IDS) will supply sequentially numbered containers containing study drug or placebo and labeled specifically for this study.
 - The IDS will prepare a randomization table for the two treatment groups and will maintain the blinding of the randomization from the study team and patients.
 - The IDS will prepare study drug and placebo to ensure blinding.
 - Each study container will contain 38 capsules.
- Dosing schedule is based on the oral dosing regimen using micronized progesterone 200 mg capsules described by Delgado and colleagues (12):
 - Study day 2-4: Two capsules orally twice daily.
 - Study days 5 through 15, 16 or 17: Two capsules orally once daily.
- Progesterone dosing comparison to dosing for approved indication:
 - Dosing for the first 3 days is double the recommended daily dose when progesterone is used orally as treatment for inducing menses in women with secondary amenorrhea (400 mg once daily for 10 days), consistent with a “high” dose initial treatment.

Recruitment:

- Potential participants will be recruited through Planned Parenthood Mar Monte (PPMM), Family Planning Associates (FPA), and the UCD Family Planning clinic.
- Women who call in to either site seeking surgical abortion or who are seen at both sites with an estimated gestational age <63 days will be informed of the study.
- Women who are interested in the study will be given a referral number to the UC Davis Family Planning Research Office.

PROTOCOL TITLE: A Randomized Trial of Mifepristone Antagonization with High-Dose Progesterone to Prevent Medical Abortion

Methodology:

Clinical Visit Procedures:

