An initial clinical visit at UCD will be required to evaluate for medical eligibility for abortion, obtain UCD consent for surgical abortion, perform transvaginal ultrasonography to confirm gestational dating (using criteria of Goldstein and Wolfson [16]) and presence of gestational cardiac activity, and confirm blood type/Rh-factor. This visit is standard care for women seeking abortion services.

Study Procedures:

- Screening visit
 - On the same day as the clinical visit or at another visit if desired, women <63 days gestation who have completed the consent process for surgical abortion will be seen in the UCD Family Planning Research office for study consent and evaluation.
 - After obtaining informed study consent, demographic information and pertinent medical history will be obtained.
- Enrollment visit
 - This visit may occur on the same day as screening if the subject is between 44 and 63 days gestation with a viable pregnancy (embryo present with gestational cardiac activity); otherwise, subject will be scheduled to return for enrollment visit when she is ≥ 44 days.
 - Subjects having an enrollment visit on a separate day from screening will have a transvaginal ultrasound repeated to confirm an embryo is present with gestational cardiac activity
 - If gestational cardiac activity not present, study physician to determine if enrollment visit should be rescheduled (if viability still possible) or if subject should be referred for clinical care of early pregnancy loss
 - Procedures
 - Confirm study eligibility
 - Two 5 mL tubes of blood will be obtained for baseline serum hCG and progesterone level.
 - Subjects will be questioned about baseline symptoms related to pregnancy (e.g., nausea, headache, mood changes).
 - Subjects will receive mifepristone 200 mg orally once all study entry criteria are confirmed (Study day 1).
 - Subjects will receive study treatment with dispensation of the next sequentially numbered study drug container. Subjects will be instructed as follows:
 - Begin study treatment on day 2, 18-24 hours after mifepristone administration (with the goal of being as close to 24 hours as possible).
 - Take the second dose on day 2 12 hours later or at bedtime (if going to bed less than 12 hours after the first dose).

PROTOCOL TITLE: A Randomized Trial of Mifepristone Antagonization with High-Dose Progesterone to Prevent Medical Abortion

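### Capsule side effects are judged against symptoms before mifepristone; no symptom record is planned before the first capsule, and the comparison has no time window

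*Combined protocol and SAP*

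**What the plan says.** Section 6 lists as a secondary tolerability endpoint "Adverse events (side effects) related to progesterone or placebo after mifepristone". In Section 7, the enrollment visit procedures state "Subjects will be questioned about baseline symptoms related to pregnancy (e.g., nausea, headache, mood changes"; this is listed ahead of the dosing step, "Subjects will receive mifepristone 200 mg orally once all study entry criteria are confirmed (Study day 1". The same section says of the diary: "The diary will also include information on baseline pregnancy symptoms (present when she started the study". A pregnancy symptom present at that time is to be entered later only if it gets worse.

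The capsules start on study day 2, 18-24 hours after mifepristone. On that day "the study site will contact the subject by phone around the time that study treatment is supposed to be started", but no symptom question is attached to the call. The regimen is two 200 mg capsules twice daily on days 2-4, then two once daily from day 5 to day 15, 16 or 17. Section 7 itself notes that "Dosing for the first 3 days is double the recommended daily dose".

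The Data Analysis Plan in Section 8 includes adverse effects among its evaluations, names chi-square and Fisher's exact tests for yes/no variables, and declares secondary outcomes unpowered and exploratory. It gives no time window or dose phase for adverse effects. Section 10 has an investigator review each adverse event for relationship to study drug.

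**The concern.** The endpoint concerns the capsules, but its reference point lies before a different drug that every woman takes first. Section 12 lists dizziness, cramping, headache, nausea and diarrhea for both drugs. A woman who becomes dizzy 10 hours after mifepristone has a new symptom relative to her diary baseline, although she has taken no capsule. In a yes/no comparison she is already an event, so dizziness later caused by progesterone adds nothing.

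Two things are at stake. The between-arm contrast is diluted and estimated with more noise. The Section 10 relatedness review also has no record of the woman's state when she took the first capsule. Separately, the absence of a time window leaves open whether the higher-dose days will be reported apart from the rest.

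**Working it through.** **The plan's own figure.** The documents give no calculation for this endpoint. The stated 20 per group (68% v 25%, alpha 0.05, beta 0.20) reproduces as 20 with the two-sided pooled-variance normal formula without continuity correction. It is used below only as the arm size, n = 20.

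**Inputs.** Mifepristone rates m and progesterone rates p from Section 12. The latter are headed "From the Prometrium label – use in premenopausal women at 400 mg/day"; none are given for the day 2-4 dose.

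**Formulas.** Assume independent effects and let every mifepristone symptom fall between mifepristone and the first capsule.
- Placebo arm: m. Progesterone arm: 1 - (1 - m)(1 - p).
- Difference with the present reference: p(1 - m). Difference with no mifepristone background: p.

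| Symptom | m | p | Progesterone arm | Difference, present | Difference, no background | Share kept |
|---|---|---|---|---|---|---|
| Dizziness | 20% | 24% | 39.2% | 19.2 | 24 | 80% |
| Cramping | 27% | 20% | 41.6% | 14.6 | 20 | 73% |
| Headache | 20% | 16% | 32.8% | 12.8 | 16 | 80% |
| Nausea | 39% | 8% | 43.9% | 4.9 | 8 | 61% |

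**No false difference.** With equal true rates in both arms, the two-sided Fisher test at 20 per arm rejects 2.4% of the time at a 39% rate and 2.3% at 20%, below the nominal 5%.

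**Fisher power at 20 per arm** (full enumeration), for the present reference, half the background removed, and all of it removed:
- dizziness 18%, 28%, 54%
- cramping 10%, 17%, 37%
- headache 9%, 13%, 21%
- nausea 3%, 4%, 2%

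No symptom reaches 80% in any case. Even with zero background, 80% power needs a difference of about 31 points.

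**If gap symptoms also mask later ones.** Suppose a woman who is already dizzy at the first capsule can never score again. With a pre-capsule reference the expected rates are then p(1 - m) = 19.2% v 0%, so the difference does not recover. Its standard error does fall:
- present: √[(0.392 × 0.608 + 0.20 × 0.80)/20] = 14.1 points
- pre-capsule reference: √[(0.192 × 0.808)/20] = 8.8 points

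Against 0 of 20, Fisher's test needs at least 5 of 20 (5 v 0 gives p = 0.047; 4 v 0 gives 0.106). Power for dizziness is P(X ≥ 5), X binomial(20, 0.192), or about 34%, against 18% now.

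**Dose phases.** Days 2-4: 4 × 200 = 800 mg/day. Day 5 onward: 2 × 200 = 400 mg/day.

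**The case against.** The strongest reply is that placebo is there to deal with exactly this. All women take mifepristone, both arms follow the same baseline rule, and the comparison is randomized and double-blind. That stands as far as bias goes: gap symptoms cannot manufacture a difference. It does not answer dilution or lost precision.

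The relatedness review in Section 10 helps in part, since an investigator could set aside a symptom known to precede the capsules. But the diary instructions do not require symptoms to be dated, and no pre-capsule status is taken, so the review may lack what it needs.

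The sizes above are fairly called an upper bound. Section 12 gives no time window for the mifepristone rates, and some of those symptoms may begin after the first capsule. The rule that a baseline symptom counts only if it worsens would remove some nausea. The label rates come without placebo rates, so they may not be wholly due to progesterone.

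A reader might infer that mifepristone swamps the endpoint. The table does not support that: 61-80% of the difference survives for these four symptoms. A reader might also infer that the plan pools the two dose phases, so that the trial cannot describe tolerability at the higher dose. The plan is silent on phases. The diary is daily, and at the day 4 (± 1 day) visit staff review it and ask about tolerance, so a split may be possible. Nor is Section 12 wrong on dose: it labels its progesterone rates as 400 mg/day, and Section 7 states that the first three days are double the 400 mg daily dose.

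**Conclusion.** The concern holds as a mismatch between the endpoint and its reference, and as an unspecified time window. Symptoms from mifepristone before the first capsule can score in both arms. At most, this takes about 5 points off the expected difference for dizziness and cramping and about 3 for headache and nausea, assuming independence, the Section 12 rates, and all mifepristone symptoms in the gap. It lowers precision but does not bias the comparison.

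The practical weight is modest. The endpoint is secondary and declared exploratory, 20 per arm is too few for it with or without the change, and the primary endpoint is untouched. The change is still worth making because these analyses are meant to show trends for a larger trial, and a pre-capsule record that was never taken cannot be reliably rebuilt. It does not deal with mifepristone symptoms that begin after the first capsule.

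**What to change.** 1. At the existing study day 2 call, timed before the first capsule, record current symptoms on a short checklist. Use that record as the reference for capsule-related side effects, counting what starts or worsens afterwards, and make it available to the Section 10 relatedness review. The call is now planned only for around the start of treatment, so its order relative to the first capsule needs to be stated.
2. Have diary symptoms dated.
3. State in the Data Analysis Plan that side effects will be tabulated by arm for three periods: day 1 to first capsule, days 2-4 after the first capsule, and day 5 onward. Note that the last period includes only women who have not exited after expulsion or loss of cardiac activity.

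The cost is a checklist on a call already planned and two extra tables, with no change to treatment, visits or sample size. The downside is small: a day 1 symptom that persists unchanged is no longer counted against the capsules.
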